15.4.1 Microbial Data

15.4.1.1 Source Data

The source data are the CFU counted for each subject at the screening baseline and treatment day baseline evaluations and at 10 minutes and 6 hours following treatment application. The data to be used in the statistical analyses will be the R values on the skin \log_{10} of the CFU/cm² of skin on the abdomen and groin. Only baseline samples with 0 time CFU counts equal to or greater than 2.0 \log_{10} for the abdomen and with 0 time CFU counts (baseline) equal to or greater than 3.0 \log_{10} for the groin will be used to determine antimicrobial efficacy.

Data from the screening baseline and treatment day baseline evaluations in each area will be averaged to determine the combined screen and baseline count for that area. Log reductions will be calculated by subtracting the post treatment log count from the average combined screen and baseline log count for that area. Additionally, log reductions will be calculated using only the baseline data from the test day.

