12.2 Baseline Week

12.2.1 The week following the pre-test period will constitute the baseline week. Subjects will not shower within forty-eight hours of being sampled. All subjects will be sampled for screening baseline at least seventy-two hours prior to treatment with the Test Articles.

12.2.2 Samples taken from the two contralateral abdominal and groin sites will be collected. Based upon adequate screening baseline count on contralateral abdominal and groin sites, a subject will be eligible to continue the study. Criteria for acceptance of screening counts will be at least 1.0×10^5 CFU/cm² on contralateral sites in the groin region and 1.0×10^3 CFU/cm² on contralateral abdominal sites. A second and final baseline sample using the same criteria as for screening baseline will be collected at each test area prior to being prepped on the day of treatment.

Post-treatment count data will be excluded from the data analysis if they are derived from any area that fails to exhibit a level of bacteria at the second baseline sampling sufficient (1.0×10^5 CFU/cm² on contralateral sites in the groin region and 1.0×10^3 CFU/cm² on contralateral abdominal sites) to permit detection of a $3.0 \log_{10}$ reduction in the groin region and a $2.0 \log_{10}$ reduction in the abdominal sites.

The table below summarizes the minimum baseline criteria for each of the test sites along with the minimum effective \log_{10} reduction criteria stipulated by the FDA.

Anatomical Site	Minimum Baseline	Minimum \log_{10} Reduction
Abdomen	1.0×10^3 CFU/cm ²	$2.0 \log_{10}$ @ 10 minutes*
Groin	1.0×10^5 CFU/cm ²	$3.0 \log_{10}$ @ 10 minutes*

*Note: 6 hour samples may not exceed the test day baseline.

12.2.3 All sample sites requiring clipping will be clipped at least forty-eight hours prior to test day.

12.2.4 All sampling will be performed using the cylinder sampling technique (Section 12.4.1).

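### Section 15.4.1.1 sets the efficacy baseline cut-off at 2.0 (abdomen) and 3.0 log10 (groin), but Section 12.2.2 excludes areas below 3.0 and 5.0 log10

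*Combined protocol and SAP*

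**What the plan says.** Section 12.2.2 sets minimum baselines of 1.0×10^3 CFU/cm² on the abdomen and 1.0×10^5 CFU/cm² in the groin. They apply at screening and again on the day of treatment: "A second and final baseline sample using the same criteria as for screening baseline will be collected at each test area". They also define the analysis set: "Post-treatment count data will be excluded from the data analysis if they are derived from any area that fails" the second-baseline requirement. The level required is described as "sufficient (1.0×10^5 CFU/cm² on contralateral sites in the groin region and 1.0×10^3 CFU/cm² on contralateral abdominal sites) to permit detection"; the reductions in question are 2.0 log10 on the abdomen and 3.0 log10 in the groin. A table in that section lists the baseline minima and the required 10-minute reductions in adjacent columns.

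Section 15.2 restricts the analysis to subjects who meet the treatment-day bacterial minimum but prints no number. Section 10.1 expects some subjects who qualified at screening to fail on the test day, so that more than 278 may have to be treated.

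Section 15.4.1.1 states the time-0 rule for efficacy differently. For the abdomen: "Only baseline samples with 0 time CFU counts equal to or greater than 2.0" log10. For the groin: "with 0 time CFU counts (baseline) equal to or greater than 3.0" log10.

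The same section defines the log reduction in two ways. One is by "subtracting the post treatment log count from the average combined screen and baseline log count for that area". The other is given as: "Additionally, log reductions will be calculated using only the baseline data from the test day". Section 15.1 treats counts below 1 CFU/cm² as 1, so the lowest log value is zero.

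**The concern.** Two sections give different numbers for one decision: whether an area's treatment-day baseline is high enough for its post-treatment counts to enter the efficacy analysis. The Section 15.4.1.1 numbers are those in the reduction column of the Section 12.2.2 table. That suggests the wrong column was carried over, although the documents do not say so.

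An analyst who builds the efficacy data set from Section 15.4.1.1 would keep areas that Section 12.2.2 excludes: baselines from 2.0 to below 3.0 log10 on the abdomen and from 3.0 to below 5.0 log10 in the groin. These areas have little or no room to show a reduction beyond the criterion, so they would limit the mean reductions reported under Section 15.4.1.3. They would also enter the covariance analyses of Section 15.4.1.4 and count towards the 111 evaluations per arm. Because Section 10.1 anticipates test-day baseline failures, such areas can be expected to arise.

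**Working it through.** **Inputs.** Baseline minima of 1.0×10^3 and 1.0×10^5 CFU/cm², and required reductions of 2.0 and 3.0 log10 (Section 12.2.2). Cut-offs of 2.0 and 3.0 log10 (Section 15.4.1.1). Floor of 1 CFU/cm² = 0 log10 (Section 15.1). Sampling volume F = 6.0 mL and cylinder area A = 3.8 cm² (Section 12.4.2).

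**1. Gap between the two rules.** Gap = log10(minimum) − cut-off.
- Abdomen: log10(10^3) − 2.0 = 3.0 − 2.0 = 1.0 log10, i.e. 1,000 against 100 CFU/cm², 10-fold.
- Groin: log10(10^5) − 3.0 = 5.0 − 3.0 = 2.0 log10, i.e. 100,000 against 1,000 CFU/cm², 100-fold.

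**2. Could units explain it?** Section 15.4.1.1 says the analysed values are log10 CFU/cm². CFU/mL would differ from that by 6.0/3.8 = 1.58, and total CFU under the cylinder by 3.8. Neither factor gives 10 or 100, and no single conversion could give both.

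**3. Headroom, test-day baseline.** With the floor at 0 log10, the largest observable reduction equals the baseline. Headroom = lowest admissible baseline − required reduction.

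| Site | Under 15.4.1.1 | Under 12.2.2 |
|---|---|---|
| Abdomen | 2.0 − 2.0 = 0 | 3.0 − 2.0 = 1.0 |
| Groin | 3.0 − 3.0 = 0 | 5.0 − 3.0 = 2.0 |

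An area at the Section 15.4.1.1 cut-off meets the criterion only if its post-treatment value is at the floor. An average of one colony per undiluted plate is 6.0 × 1/3.8 = 1.58 CFU/cm², or 0.198 log10. The reduction is then at most 2.0 − 0.198 = 1.80 (abdomen) or 3.0 − 0.198 = 2.80 (groin), short of the criterion.

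**4. Headroom, combined baseline.** Screening already requires 3.0 and 5.0 log10. Averaging the two baselines on the log scale, the lowest combined baseline under Section 15.4.1.1 is (3.0 + 2.0)/2 = 2.5 on the abdomen and (5.0 + 3.0)/2 = 4.0 in the groin. Headroom is 2.5 − 2.0 = 0.5 and 4.0 − 3.0 = 1.0, against 1.0 and 2.0 under Section 12.2.2.

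**5. Illustration of size.** Let f be the share of analysed areas admitted only by Section 15.4.1.1; the documents give no value for it. Put those areas at the Section 15.4.1.1 cut-off and all others at the Section 12.2.2 minimum. The mean of the largest observable test-day reductions then falls by f × (3.0 − 2.0) on the abdomen and f × (5.0 − 3.0) in the groin.

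| Assumed f | Abdomen (log10) | Groin (log10) |
|---|---|---|
| 0 (12.2.2 applied) | 0 | 0 |
| 5% | 0.05 | 0.10 |
| 10% | 0.10 | 0.20 |
| 20% | 0.20 | 0.40 |

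This is a fall in the ceiling, not in the expected mean reduction.

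**6. Sample size.** The formula in Section 10.1 reproduces: 0.735² × (1.96 + 0.842)² / 0.196² = 110.41, rounded up to 111. It contains no baseline threshold, so correcting Section 15.4.1.1 leaves it unchanged.

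**The case against.** The strongest reply is that the plan already controls this. Section 12.2.2 is an explicit analysis-exclusion rule. Section 15.2 precedes Section 15.4.1.1 and can only be pointing to Section 12.2.2, because the inclusion list in Section 10.2 contains no bacterial level. The wording of Section 15.4.1.1 is a necessary condition; it does not promise to keep every sample above the cut-off. Read together, the stricter rule binds and the looser one does nothing. This stands: applied as a whole, the plan gives the Section 12.2.2 analysis set. It does not rescue the printed numbers, which then exclude nothing, misstate the criterion, and are the only numbers available to a reader looking in Section 15 for the figure that Section 15.2 omits.

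Three further points stand in part:
- The share f is assumed, and other areas may start above the minimum. The illustration therefore bounds neither the loss of ceiling nor the real effect.
- Section 15 plans no test against the 2.0 and 3.0 log10 criteria. The paired tests compare baseline with post-treatment counts, and the between-treatment analysis adjusts for baseline, although a covariate would not fully remove a ceiling. The exposure is mainly in the reported means, and in a direction that does not flatter the product.
- The sections also differ in the unit excluded: area in Section 12.2.2, subject in Section 15.2, sample in Section 15.4.1.1. Correcting the numbers does not settle that. It is a separate matter and does not make the numerical correction unsound.

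**Conclusion.** The concern holds. Section 15.4.1.1 is wrong as written: its cut-offs contradict the plan's own exclusion rule by 1.0 log10 on the abdomen and 2.0 log10 in the groin, and equal the required reductions. No unit conversion reconciles them. At those cut-offs the test-day headroom over the criterion is zero at both sites.

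The consequence is conditional. It is nil if Section 12.2.2 is applied, and arises only if Section 15.4.1.1 is taken as the governing rule. Neither the number of areas affected nor the change in mean reductions can be derived from the documents. The cut-off is applied to pre-treatment counts and is common to all arms, so no bias towards any arm is claimed. This should be fixed before the efficacy data set is programmed.

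**What to change.** In Section 15.4.1.1, replace 2.0 and 3.0 log10 with the Section 12.2.2 treatment-day minima, 3.0 log10 for the abdomen and 5.0 log10 for the groin. Sections 12.2.2, 15.2 and 15.4.1.1 then rest on one numerical criterion. A cross-reference to Section 12.2.2 in the same sentence would be sensible, and the unit of exclusion can be stated there.

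The cost is a one-sentence wording change. Screening and test-day sampling already use the higher thresholds, so the design, sampling and sample size are unaffected.

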15.4.1.2 Analysis of Baseline Data

- The average combined screening baseline and treatment day baseline \log_{10} CFU of the test products will be compared using analysis of variance techniques.
- The baseline \log_{10} CFU from the test day will be compared using analysis of variance techniques.

15.4.1.3 Within-Treatment Analysis

- The average combined screening baseline and treatment day baseline \log_{10} CFU will be compared to the \log_{10} CFU at the 10-minute and 6-hour post treatment evaluations utilizing Student's t-test for paired data.
- The \log_{10} CFU at the treatment day baseline will be compared to the \log_{10} CFU at the 10-minute and 6-hour post treatment evaluations utilizing Student's t-test for paired data.

Summary statistics will consist of mean \log_{10} CFU (\pm 95% CI) and mean \log_{10} CFU differences (\pm 95% CI) expressed as geometric mean \log_{10} reductions.

15.4.1.4 Between-Treatment Analysis

- Differences between the test products will be evaluated at the 10-minute and 6-hour post treatment evaluations using analysis of covariance techniques with the average combined screening baseline and treatment day baseline \log_{10} CFU as the covariate.
- Differences between the test products will be evaluated at the 10-minute and 6-hour post treatment evaluations using analysis of covariance techniques with the treatment day baseline \log_{10} CFU as the covariate.

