12.3 Test Period

12.3.1 Prior to being sampled, the subjects will be questioned regarding their adherence to protocol restrictions. Subjects will be visually examined again (by a technician) at the anatomical sampling sites to ensure no evidence of injury or dermatoses is present.

12.3.2 Randomization: According to a computer-generated randomization schedule, test areas on each subject's groin and abdominal regions will be delineated to receive one of the five test articles on each side. Randomization will be balanced between left and right sides. Treatment day baseline and post prep sampling sites will be randomized within each test area.

12.3.3 Blinding: The test material cannot be blinded from the investigator because of the obvious difference in applicator design and color. The investigator treating the subject will not be involved in bacterial enumeration and counting the plates of that particular subject.

12.3.4 The dimensions of each treatment area will be 2" x 5" on the upper inner part of the thigh below the inguinal ligament. The dimension of each treatment area will be 5" x 5" on side of umbilicus on the abdomen. Four sampling sites will be delineated within each treatment area.

[figure not shown]
12.3.5 Based upon the design stipulated in the Section 6.0, the groin region and abdomen will be sampled for the final baseline (second baseline). The appropriate areas will be prepped using the test articles (Appendix 1). The sites will be sampled as stipulated in Section 6.0.

12.3.6 For the 6 hour \pm 30 minutes sites, sterile gauze pads will be placed over the prepped areas to aid prevention of microbial contamination. The gauze pads will be held in place with an occlusive sterile catheter dressing. All samples will be taken from sites using the cylinder sampling technique (Section 12.4.1).

NOTE: Timed sampling will begin when prepping is completed as defined in the instructions for prepping (See Appendix 1).

Diagrams of the treatment regions are provided below:

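### Left/right side is balanced and sampling position randomized by design, but the between-treatment ANCOVA names neither: a small, inexpensive gain in precision

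*Combined protocol and SAP*

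**What the plan says.** Section 12.3.2 has each subject's groin and abdominal areas "delineated to receive one of the five test articles on each side". It adds: "Randomization will be balanced between left and right sides". Within an area, "Treatment day baseline and post prep sampling sites will be randomized within each test area", and Section 12.3.4 states: "Four sampling sites will be delineated within each treatment area". So side is a balancing factor. Position is randomized, but is not said to be balanced across articles.

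Section 15.4.1.4 specifies two between-treatment analyses: "Differences between the test products will be evaluated at the 10-minute and 6-hour post treatment evaluations using analysis of covariance techniques". One adjusts for the average of the screening and treatment-day baselines, the other for the treatment-day baseline alone. Section 15 does not name side or position as a model term. It does not write the model out in full either, so the terms are unmentioned rather than expressly excluded.

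The baseline is specific to the treated area: Section 15.4.1.1 forms the combined baseline separately for each area, and Section 12.2.2 collects the treatment-day baseline at each test area.

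**The concern.** A factor used to balance the randomization normally appears in the analysis. If it affects the outcome and is left out, its variation sits in the residual although the design has already removed it from the article contrast, so the reported SE is slightly too large.

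Position works a little differently. The baseline and post-prep samples are allotted among the four sites in an area, so a position effect need not cancel between them. It adds variation to the outcome and noise to the covariate. Because position is only randomized, the unadjusted SE is still honest, but it is larger than it need be.

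What is at stake is the width of the confidence intervals for article differences at 10 minutes and 6 hours. Validity is not at stake, because balance and randomization protect against bias from either source.

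**Working it through.** **Inputs from Section 10.1:** SD 0.735 log10, difference 0.196 log10, Z values 1.96 and 0.842, 111 evaluations per arm, five arms.

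**The plan's own figures.** n = 0.735² × (1.96 + 0.842)² / 0.196² = 110.41, rounded up to 111. Subjects: 5 × 111 / 2 = 277.5, rounded up to 278. Both reproduce, and neither depends on this point. Evaluations per region: 5 × 111 = 555.

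**Assumed inputs.** The documents give no side or position effect. I take a left-right shift d of 0.1 to 0.3 log10 and an SD among position means p of 0.05 to 0.2 log10.

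**Step 1: simple bound, ignoring the baseline covariate.** A balanced shift d contributes variance d²/4 and position contributes p². The adjusted SD is √(0.735² − d²/4 − p²). The unadjusted 95% half-width for a two-arm difference is 1.96 × 0.735 × √(2/111) = 0.1934.

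| d, p | variance removed | share of 0.5402 | adjusted half-width | unadjusted wider by |
|---|---|---|---|---|
| 0.1, 0.05 | 0.0050 | 0.9% | 0.1925 | 0.5% |
| 0.2, 0.1 | 0.0200 | 3.7% | 0.1898 | 1.9% |
| 0.3, 0.2 | 0.0625 | 11.6% | 0.1818 | 6.3% |

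For side alone (p = 0) the excess is 0.2%, 0.9% and 2.2% at d = 0.1, 0.2 and 0.3.

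**Step 2: with the area's own baseline in the model.** I simulated the ANCOVA with 280 subjects, two articles each, article pairs balanced over sides, and the side shift present at baseline and afterwards. Assumed SDs: subject 0.4, area 0.3, baseline sampling 0.3, post-treatment sampling 0.45. The table shows how much larger the SE of an article difference is without the terms than with them; a negative entry means that adding the terms costs precision.

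| d, p | side (1 df) | side + post-treatment position (4 df) | side + both positions (7 df) |
|---|---|---|---|
| 0, 0 | 0.0% | −0.3% | −0.5% |
| 0.1, 0.05 | 0.03% | 0.5% | 0.4% |
| 0.2, 0.1 | 0.1% | 2.6% | 3.3% |
| 0.3, 0.2 | 0.5% | 10% | 13% |

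The baseline absorbs most of a stable left-right shift: at d = 0.3 the excess falls from 2.2% in Step 1 to 0.5%. It does not absorb position, so nearly all of the gain comes there. The last row exceeds the 6.3% of Step 1 because the simulated residual SD is smaller than 0.735. It is √(0.4525 − 0.25²/0.34) = 0.518, from outcome variance 0.4525, baseline variance 0.34 and covariance 0.25. A given position effect is therefore a larger share of it.

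**Degrees of freedom:** 1 for side + 3 + 3 for two four-level positions = 7.

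**The case against.** The strongest reply is that nothing in the documents shows that side or position matters. A reader might infer that the omission widens every comparison, or that the SEs are larger than the design allows. The documents do not support that: with no true effect nothing widens, and the extra terms cost a fraction of a percent. This stands, so every size given here is conditional.

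Second, the area-specific baseline already deals with most of a lasting left-right difference. That also stands and leaves side worth very little numerically. In the paired tests of Section 15.4.1.3, side is constant within an area and cancels.

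Third, position is randomized but not stated to be balanced, so adjusting for it is optional. This is correct. A reader might also suppose a gradient along the groin area towards the inguinal fold. Section 12.3.4 gives the area as 2 by 5 inches below the inguinal ligament, but the text states neither its orientation nor the arrangement of the four sites, and the diagrams are not reproduced. The gradient is conjecture.

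Fourth, the wording of Section 15.4.1.4 is loose enough to allow further terms. That does not remove the point: an unspecified model leaves the choice of terms open until the data are seen.

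**Conclusion.** The point holds as a minor one about precision. Section 12.3.2 uses side as a balancing factor and randomizes position; the ANCOVAs in Section 15.4.1.4 name neither. If either affects counts beyond what the area's baseline captures, the comparisons are slightly conservative or less precise than they could be.

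Under the assumed effects, the unadjusted SE is at most about 0.5% too large for side alone and about 0.5% to 10% for side with post-treatment position. The upper end needs a position SD of 0.2 log10, for which the documents give no evidence. These figures also depend on the assumed variance components.

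There is no bias. The within-arm criteria in Section 12.2.2 (2.0 and 3.0 log10 reductions at 10 minutes, 6-hour counts not above baseline) do not depend on this ANCOVA. Whether the model needs a subject term, since each subject receives two articles, is a separate question.

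**What to change.** In Section 15.4.1.4, write out both ANCOVA models. Include side (left/right) as a fixed factor because the randomization is balanced on it. Where the randomization schedule or sampling records hold the position, also prespecify the position of the post-treatment sample and the position of the treatment-day baseline sample as four-level fixed factors. If position is left out, say so.

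Section 13.0 provides for sampling records but does not say that position is recorded, whereas Appendix 2, Section 5.2 expressly requires site location for the neutralization study. The data collection forms should be checked on this.

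The cost is a line or two of text and at most 7 degrees of freedom out of about 550 evaluations per region. If there is no true effect, the SE rises by about 0.3% with side and post-treatment position, or about 0.5% with all seven terms. One limit remains: the combined-baseline covariate also includes the screening sample, whose position these factors do not cover.

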2.0 OBJECTIVE

The purpose of this study is to compare the antimicrobial effectiveness potential of three investigational test products identified as "ChloraPrep Triple Swabsticks" using two application procedures (three swabsticks at once and the three swabsticks used sequentially). "Hibiclens" will be evaluated to serve as the reference product (positive control). "Sterile Triple Swabsticks Saturated with 5.25 mL of Sterile Deionized Water" ("Sterile Swabsticks with Sterile Deionized Water") using two application procedures (three swabsticks at once and the three swabsticks used sequentially) will be evaluated to serve as a negative control. This evaluation will be conducted based on methodology specified by the Food and Drug Administration Office of Drug Evaluation and Research.

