6.0 SCOPE

This evaluation will measure the antimicrobial effectiveness of a preoperative skin product as specified by the Food and Drug Administration Tentative Final Monograph (TFM) for *Effectiveness Testing of a Patient Preoperative Skin Preparation* (FR 59:116, 17 June 94, pp. 31450-31452).

This study will evaluate the antimicrobial effectiveness of the three test and control articles: "ChloraPrep Triple Swabsticks" using two application procedures (three swabsticks at once and the three swabsticks used sequentially), "Hibiclens", and "Sterile Swabsticks with Sterile Deionized Water" using two application procedures (three swabsticks at once and the three swabsticks used sequentially). A minimum of 278 human subjects will be employed utilizing bilateral product applications assuring that the each test and control articles will be evaluated on sites as described in the following table.

Test Articles (Application)	Number of Evaluations on Abdomen	Number of Evaluations on Groin
ChloraPrep Triple Swabsticks (three swabsticks applied all at once)	111	111
ChloraPrep Triple Swabsticks (three swabsticks applied sequentially)	111	111
Hibiclens (applied according to package directions)	111	111
Sterile Swabsticks with Sterile Deionized Water (three swabsticks applied all at once)	111	111
Sterile Swabsticks with Sterile Deionized Water (three swabsticks applied sequentially)	111	111

Each of the test articles will be evaluated at the groin and the abdominal sites for immediate antimicrobial effect by sampling at ten minutes \pm thirty seconds and six hours \pm thirty minutes after completion of application. All product applications will be performed using randomized placement.

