10.0 SUBJECT SELECTION

10.1 Number of Subjects

The requirement of 111 subjects per test article configuration (test arm) to finish this study was determined by the sample size equation at the recommendation of both the FDA Proposed Rule and ASTM E1173; the following formula was used for group size calculations:

$$n \geq s^2 \frac{(Z_{\alpha/2} + Z_{\beta})^2}{\Delta^2}$$

Where:

- n = minimum number of required samples in each test arm (rounded up).
- s = standard deviation of the acquired data (0.735).
- $Z_{\alpha/2}$ = the Z statistic for a two-sided 95% confidence interval (1.96), where α (0.05) is the probability of allowing a Type I error (predicting significance when there is none).
- Z_{β} = the Z statistic for the power of the test (0.842), where β (0.80) is the power, i.e., the probability of allowing a Type II error (failing to predict significance when it exists).
- Δ = the difference being tested for (0.196).

The best reasonable estimate of the number of subjects needed per test article configuration (study arm), based on available current data is 111.

Since there are five study arms, the minimum number of subjects based on bilateral applications is 278 (Five arms x 111 / 2).

Initial screening baseline counts will be collected from a number of healthy subjects of at least the age of sixteen sufficient to provide at least 278 qualified subjects to enter the treatment phase of the study. (NOTE: As it is anticipated that not all subjects that have qualifying screening-day baseline counts will have qualifying test-day baseline counts, it may be necessary to treat more than 278 subjects.)

The eligibility of each subject will be determined from a medical history collected on the Screening Inclusion/Exclusion Form and Treatment Inclusion/Exclusion Form (to be provided prior to study initiation).

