15.0 DATA AND STATISTICAL ANALYSIS

The analyses outlined below will be conducted on the data generated.

- 15.1 Raw data (CFU/mL) will be converted to \log_{10} CFU/cm². Counts of less than 1 CFU /cm² will be treated as 1 CFU/cm² such that the log transformation will be zero. Log reductions will be calculated by subtracting the post treatment log counts from the treatment day baseline counts obtained.
- 15.2 Only subjects who meet the minimum inclusion criteria for levels of bacteria on the treatment day of the study will be included in the analysis with the following exception: lab accidents resulting in contaminated samples. If there are missing data at some but not all time points, data from the available times will be included in the analysis.
- 15.3 Any subject with missing data will not be included in the data analysis. The subject with missing data will be replaced with a new subject.
- 15.4 Separate statistical analyses will be conducted for data collected from the abdomen and the groin. All hypothesis testing will be conducted at the alpha=0.05 level of significance. Data will be presented in tabular and graphical format.

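### Both sides of each subject are treated, but the between-article ANOVA and ANCOVA name no subject term and Kruskal-Wallis assumes independent groups, so within-subject information is lost by an amount the documents do not fix

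*Combined protocol and SAP*

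**What the plan says.** The objective in section 2.0 is comparative: "The purpose of this study is to compare the antimicrobial effectiveness potential of three investigational test products". The design is bilateral. Section 6.0 states "A minimum of 278 human subjects will be employed utilizing bilateral product applications", and section 10.1 derives the total the same way: "the minimum number of subjects based on bilateral applications is 278", from five arms of 111 divided by two. Under 12.3.2, "test areas on each subject's groin and abdominal regions will be delineated to receive one of the five test articles on each side", with left-right balance. That section does not say whether one subject's two sides must receive different articles, or how often each pair of articles occurs.

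The between-article analyses are these:
- 15.4.1.2: baselines are compared by analysis of variance techniques.
- 15.4.1.4: post-treatment counts are compared "using analysis of covariance techniques with the treatment day baseline" as covariate, and in a parallel analysis with the combined screening and treatment-day baseline.
- 15.4.2.3: changes in irritation score, averaged over the two times, are compared by Kruskal-Wallis.

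None of these mentions subject, block, random effect or repeated measures. The paired t-tests (15.4.1.3) and signed-rank tests (15.4.2.2) compare baseline with post-treatment within one article. They do not use the left-right pairing.

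**The concern.** Two evaluations on one person are likely to be correlated. An analysis that treats all evaluations as independent reports a standard error that does not match the design and ignores the comparison of two articles within the same person, which bilateral treatment makes possible. These are the analyses that serve the stated purpose, so what is at stake is the precision of the article contrasts and the ability to see irritation differences, a safety outcome. How articles are paired across sides decides whether the reported standard error is too large, about right or too small, and the plan leaves that open.

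**Working it through.** **Inputs from the documents.** SD 0.735, difference 0.196, Z values 1.96 and 0.842, 111 per arm, five arms, two sides per subject (10.1, 6.0); alpha 0.05 (15.4).

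**Plan's own figures.** 0.735² × (1.96 + 0.842)² / 0.196² = 110.4, rounded up to 111. Then 5 × 111 / 2 = 277.5, rounded up to 278. Both reproduce.

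**Input not in the documents.** Rho, the left-right correlation of residuals within a subject. The range 0.1 to 0.7 is assumed.

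**(a) Different articles on the two sides, ten pairs equally frequent, no covariate.** Variances are in units of 2s²/n.
- Subject ignored: each pair of articles shares about a quarter of its subjects, so the true variance is 1 − rho/4. The model reports about 1.
- Subject as random effect: the efficiency factor is 5 × 1 / (4 × 2) = 0.625, so the variance is 1 / [0.625/(1 − rho) + 0.375/(1 + rho)] = (1 − rho²)/(1 + rho/4).
- Unblocked pairwise alpha: 2[1 − Φ(1.96/√(1 − rho/4))].

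| rho | true variance, subject ignored | variance, subject in model | cut in true variance | fall in true SE | CI narrower than unblocked model reports | unblocked pairwise alpha |
|---|---|---|---|---|---|---|
| 0.1 | 0.975 | 0.966 | 1% | 0.5% | 2% | 0.047 |
| 0.2 | 0.950 | 0.914 | 4% | 2% | 4% | 0.044 |
| 0.3 | 0.925 | 0.847 | 8% | 4% | 8% | 0.042 |
| 0.5 | 0.875 | 0.667 | 24% | 13% | 18% | 0.036 |
| 0.7 | 0.825 | 0.434 | 47% | 27% | 34% | 0.031 |

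The two precision columns have different reference points. The fall in true SE is 1 − √(ratio of the two variances). The CI column is 1 − √(variance with subject), against the model-reported value of 1.

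An ANCOVA simulation with own-side baseline (4,000 data sets per rho; assumed slope 0.4, baseline SD 0.6, left-right baseline correlation 0.6, residual SD 0.735) gave cuts of 0.5%, 3.8%, 8.4%, 23.7% and 46.4%. Unblocked alpha fell from 0.047 to 0.030; mixed-model alpha was 0.050 to 0.053.

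**(b) Sides randomized independently.** Simulated unblocked alpha is 0.049 to 0.054; the cuts are about 1%, 4%, 8%, 25% and 49%.

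**(c) Same article always on both sides (extreme).** Pairwise alpha is 2[1 − Φ(1.96/√(1 + rho))]: 0.062 at rho 0.1 and 0.110 at 0.5. The overall five-article test is worse: simulated ANOVA alpha is 0.178 at 0.5.

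**What shrinks the gain.** With own-side adjustment, residual rho = (raw rho − c²·rb)/(1 − c²), where c is the baseline-to-post correlation and rb the left-right baseline correlation. Assuming c = 0.3 to 0.5 and rb = 0.6 to 0.8:
- Raw rho 0.2 becomes at most (0.2 − 0.09 × 0.6)/0.91 = 0.16, a cut of 1 − [(1 − 0.0256)/1.04]/0.96 = 2.4%. It reaches zero at c = 0.5, rb = 0.8: (0.2 − 0.25 × 0.8)/0.75 = 0.
- Raw rho 0.5 becomes 0.20 to 0.49, if cases where both sides' baselines matter equally are included. At 0.49 the cut is about 23%.

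The rule in 15.1 for counts below 1 CFU/cm², "such that the log transformation will be zero", trims it further. At latent rho 0.5 with 10%, 26% or 40% of chlorhexidine values at zero, the simulated cut is 25%, 22% or 19%.

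**Irritation.** Under case (a) with normal data, simulated Kruskal-Wallis alpha is 0.042, 0.028 and 0.021 at rho 0.3, 0.5 and 0.7. Power depends on a score scale and frequencies that are not given. With one assumed graded scale, Kruskal-Wallis against a rank mixed model gave 0.52 vs 0.57 at latent rho 0.3 and 0.49 vs 0.63 at 0.5. With sparser assumed scores it gave 0.26 vs 0.29 and 0.24 vs 0.30.

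**The case against.** The strongest defence is that 15.4.1.2 and 15.4.1.4 speak of techniques, which does not exclude a subject term. This stands: for those sections the fault is that the model is left open. It does not cover 15.4.2.3, where Kruskal-Wallis is fixed by name.

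Second, validity is not threatened on natural readings of 12.3.2, and the gain may be small because the side-specific baseline already absorbs part of the subject effect. This also stands. It limits the point to precision, and the range properly starts at nil.

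Third, the minimum log-reduction criteria in 12.2.2 are within-article. Their point estimates are indeed unaffected. The accompanying tests and intervals in 15.4.1.3 are unaffected only when the two sides carry different articles. With independent randomization about one subject in five (5 × 1/25) would have the same article on both sides.

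A reader might infer that ignoring subject inflates type I error and makes the comparisons invalid. The documents do not support that. Inflation requires the same article to tend to fall on both sides, an arrangement 12.3.2 neither suggests nor excludes.

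**Conclusion.** The point holds as one of precision. Run as named, the between-article analyses discard within-subject information: the tests are conservative with different articles on the two sides and about nominal with independent sides. With different articles and residual rho of 0.1 to 0.7, the cut in true variance forgone is about 1% to 47%. For raw rho up to 0.5, after baseline adjustment, it runs from nil to about 23%. These figures rest on an assumed correlation and nearly balanced pairs; no single loss can be stated.

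Two further inferences should be resisted. The irritation power figures are illustrative and not estimates for this trial. Whether 111 per arm is enough is a separate sample-size question that this point does not settle. The change should be made because it is cheap and best settled before data exist, not because the planned tests would be invalid.

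**What to change.** 1. In 15.4.1.4, for each body site and time, specify a linear mixed model with article as fixed effect, the stated baseline as covariate (treatment-day in one analysis, combined in the other) and subject as random effect. Report article contrasts with 95% confidence intervals. In 15.4.1.2 use the same model without the covariate.
2. In 15.4.2.3 replace Kruskal-Wallis with one method that respects subject, for example ranking the averaged changes over all areas of a body site and fitting article as fixed and subject as random effect.
3. In 12.3.2 state that a subject's two sides receive different articles, with the ten article pairs as nearly balanced as possible while keeping at least 111 evaluations per article. With exactly 278 subjects, eight pairs occur 28 times and two occur 27 times (8 × 28 + 2 × 27 = 278). The two short pairs must share no article. Each article is in four pairs, so one that falls in both short pairs gets 2 × 28 + 2 × 27 = 110. This happens in 30 of the 45 possible choices. Replacements and extra treated subjects (10.1, 15.3) will alter exact counts, so write the rule as near balance with a floor of 111.

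The cost is plan wording, one sentence on the schedule and slightly more analysis work in standard software, with no extra subjects, data or procedures. If rho is near zero, little or nothing is gained. Simulated power is not lost either: at rho 0 with normal data, the rank mixed model gave 0.713 against 0.710 for Kruskal-Wallis.
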